7.1 Sample Size Determination

This is a pilot study to obtain pilot data for larger studies. Previous observational studies in humans suggest at least a moderate effect of ovarian hormones on binge eating with an effect size approximating $d = 1.5$,^{5, 196, 197} including [name] pilot work described above. Additionally, [name] pilot work of E2 treatment in midlife women indicates $d = 2.3$ for the effect of E2 replacement decreasing appetite in women with and without major depression whereas other published work showed $d = 1.51$ for the effect of Lupron on decreasing food cravings in women with PMS.⁸⁷ Because we are directly manipulating ovarian hormones with an experimental design, which removes other potential confounds found in observational studies, we expect that the effect sizes from observational studies are an underestimate.

According to a power estimation for Aims 1 and 2, with a projected sample of $n = 15$, an effect size of .77 is required to detect a treatment difference at a two-sided .05 significance level at 80% power (calculated based off of projected sample size and desired power). Additionally, based on $n = 15$ and estimated effect size of 1.5 for E2 on binge eating (the average effect size observed in previous studies),^{5, 196, 197} a power estimation for Aim 1 (our primary aim) estimates our power at significance of .05 is $> 90\%$. Thus, despite the smaller sample size of this pilot study, power analyses indicate we should have sufficient power based on hypothesized effect sizes (which are empirically based) for E2 on binge eating.

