The BIS/BAS and SPSRQ will be included as a self-report measures of reward response. Specifically, we will include the reward responsiveness, behavioral inhibition, and fun seeking subscales of the BIS/BAS as self-report correlates of the reward response. The SPSRQ will be used to assess sensitivity to reward.

Hypothesis. Our overarching hypothesis for the following aims is that BN represents a hormone sensitive phenotype and this sensitivity is displayed as an impaired reward response within the context of low E2 such that E2 addback will be beneficial for all outcomes of interest (i.e., binge eating, aspects of the reward response). As such, our null hypothesis is that there is no effect of E2 on binge eating or the reward response. For all hypothesis tests, we will use the Benjamini-Hochberg Procedure to correct for multiple comparisons.

Aim 1: Quantify the direct effect of E2 and P4 on binge eating in women with BN.

Dependent variables: EPSI binge eating subscale score; DSRP binge eating weekly average.

Independent variables: Treatment sequence, treatment condition, and selected covariates

The two longitudinal measures of binge eating (i.e., EPSI subscale score and DSRP weekly average) will be fit to linear mixed effect models with subject-specific random intercept assuming an unstructured covariance among different time points. Such a covariance allows different variance and covariance parameters to be estimated for each time point allowing for potential increasing or decreasing variability in outcomes during each of the follow-up time points for each outcome and will include fixed effect predictors such as binary treatment sequence (E2-P4 or P4-E2) and treatment condition of categorical variable with three levels: Lupron-alone, E2, or P4, where effect size and standard error of fixed effect parameters will be estimated in the described model followed by t -test. Study hypotheses comparing outcomes between group outcomes of E2 vs. Lupron-alone, E2 vs. P4, and P4 vs. Lupron-alone, will be tested using contrasts test through t -test of least squares means estimate in the context of the main effects model.

Along with the primary contrasts of interest described above, additional contrasts between each end point of treatment condition (Lupron-alone, E2, or P2) and baseline (T1), which occurs prior to medication administration, will be tested using the statistical model just described above.

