Aim 2: Determine the effect of E2 on reward response and related correlates (e.g., behavioral inhibition) in women with BN.

Dependent variables: Behavioral measures of reward response, self-report measures of reward response.

Independent variables: Treatment sequence, treatment condition, and selected covariates

Behavioral measures of reward response (MID, DD) and related correlates (Go No/Go, BIS/BAS, SPSRQ) will be fit to linear mixed effect models as described above with binary treatment sequence (E2-P4 or P4-E2), treatment condition, and covariates as independent variables and reward response as dependent variables. The contrasts between E2 and baseline (T1) or Lupron-alone (T2) will be tested in the same model.

For the behavioral tasks, beneficial impacts of E2 are defined as an accelerated speed of response to rewards and improvement in reward learning during the MID, higher indifference points during the DD task, and fewer errors on the Go No/Go Task. For self-report questionnaires, a decrease in scores represents a beneficial response as higher scores indicate more “pathological” responses.

Aim 3: Examine the association between reward response (defined in Aim 2) and binge eating before and after E2 addback.

Null hypothesis: There is no association between reward response and binge eating before and after E2 addback
Alternative hypothesis: There is an association between reward response and binge eating before and after E2 addback.

We will explore Pearson correlations between change in self-reported reward responses and change in binge eating between baseline and E2 addback. Binge eating will be defined by the EPSI subscale score. Reward response will include the BIS/BAS reward responsiveness subscale, and SPSRQ reward sensitivity subscale. Specifically, a change score will be created that signifies the amount and direction of change that occurred in binge eating and reward responses between baseline and E2 addback for each subject. A Pearson correlation will then be examined between binge eating and reward response change scores.

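### Section 7.1's 80% power at d = .77 describes one unadjusted contrast, not the Benjamini-Hochberg-corrected tests of Aims 1 and 2, and the d = 1.5 behind its second power figure is credited to human observational studies although two of its three references are rat experiments by title

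*Combined protocol and SAP*

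**What the plan says.** Section 7.1 makes two power statements.

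- For Aims 1 and 2 together, with 15 women, "an effect size of .77 is required to detect a treatment difference at a two-sided .05 significance level at 80% power". Multiplicity is not mentioned.
- For Aim 1, power exceeds 90% at an effect of 1.5, described as "the average effect size observed in previous studies" and referenced to items 5, 196 and 197. The opening of the section cites the same three items, together with pilot work: "Previous observational studies in humans suggest at least a moderate effect of ovarian hormones on binge eating with an effect size approximating" 1.5. It then reasons that, because this trial manipulates hormones directly, "we expect that the effect sizes from observational studies are an underestimate".

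Section 7.2 sets the multiplicity rule: "For all hypothesis tests, we will use the Benjamini-Hochberg Procedure to correct for multiple comparisons". It gives neither q nor the family of tests. The tests it lists are:

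- Aim 1, on two binge-eating outcomes: "Study hypotheses comparing outcomes between group outcomes of E2 vs. Lupron-alone, E2 vs. P4, and P4 vs. Lupron-alone", plus a contrast of each condition with baseline.
- Aim 2, on each reward measure: "The contrasts between E2 and baseline (T1) or Lupron-alone (T2) will be tested in the same model".

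**The concern.** A reader takes .77 as the effect that any test under Aims 1 and 2 can detect with 80% power. If the figure ignores the correction that 7.2 imposes, it answers a different question, and the plan leaves open what the reader needs to convert it.

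The second statement carries the section's conclusion of sufficient power, and it depends entirely on d = 1.5. If that value is said to come from women observed over the menstrual cycle while most of its references are animal experiments, its relevance cannot be judged. Section 1.1 itself doubts that animal findings carry over to human behaviour. The trial is also meant to guide larger studies, so a mislabelled effect size could be carried forward.

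**Working it through.** **1. Reproduce the plan's figures.** Inputs from 7.1: n = 15, two-sided .05, d = .77. The design is within-subject, so take d as dz, the mean difference divided by the SD of differences, and use a paired t-test with df = 14.

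- Noncentrality = dz × √n = .77 × √15 = 2.98; critical t = 2.145.
- Power = 79.2%. The dz for exactly 80% is 0.778. The stated figure therefore reproduces as **one unadjusted contrast with 15 completers**.
- At d = 1.5, noncentrality = 1.5 × √15 = 5.81 and power = 99.97%, so the claim of more than 90% also reproduces.

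**2. Count the tests the correction could cover.**

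- Aim 1: 2 outcomes × 3 main contrasts = 6. The baseline contrasts add 2 × 3 = 6, giving 12.
- Aim 2: 7 outcomes (MID, DD, Go/No Go, three BIS/BAS subscales, SPSRQ reward) × 2 contrasts = 14, giving 26.
- Aim 3's two correlations would make 28.
- Correcting within one Aim 1 outcome gives 3.

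Every one of these families has more than one test. At q = .05 no BH cut-off exceeds .05, so power per test cannot exceed the unadjusted figure for the same df.

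**3. Settle what the model implies for df.** Section 7.2 names both a random intercept and an unstructured covariance. A per-contrast paired analysis has df 14. A random-intercept model on three conditions has df (15 − 1) × (3 − 1) = 28, and unadjusted power at .77 is then 82.1%.

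**4. Respect the structure of the contrasts.** The three Aim 1 contrasts are linearly dependent:

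E2 − Lupron = (E2 − P4) + (P4 − Lupron).

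Two patterns are therefore ruled out for one outcome.

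- All three contrasts at dz = .77. The largest mean difference equals the sum of the other two, so its SD would have to equal the sum of their SDs, which requires perfectly correlated differences.
- Exactly one real effect. If two of the mean differences are zero, so is the third.

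Two patterns that can occur are an E2 effect of .77 with P4 equal and opposite, and an E2 effect of .77 with no P4 effect.

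**5. Simulate BH on that structure.** Three or six tests (one or two outcomes), with equal SDs. Power for E2 versus Lupron-alone at .77, good to about one percentage point:

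| q (assumed) | P4 effect | df 14 | df 28 |
|---|---|---|---|
| .05 | equal and opposite | about 77–78% | about 81–82% |
| .05 | none | about 67–70% | about 72–74% |
| .10 | either | about 79% or more | about 79% or more |

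**6. Test the second power statement against correction.** Paired t, n = 15, df 14. The thresholds .05/6 and .05/26 are the strictest BH steps for 6 and 26 tests:

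| d | .05 | .05/6 | .05/26 |
|---|---|---|---|
| 1.5 | 99.97% | 99.2% | 95.3% |
| 1.0 | 95% | 77% | 55% |
| 0.5 | 44% | 18% | 7% |

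Counting Aim 3 (.05/28) gives 94.9% at d = 1.5.

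**7. Set the source of 1.5 beside its references.** By the titles in section 10:

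- Item 5 concerns ovarian hormones and binge eating in bulimia nervosa. Section 1.4 reports it as phase Z-score means and regression coefficients, not as d = 1.5.
- Item 196 concerns ovariectomy in adult female rats.
- Item 197 concerns estradiol and progesterone in ovariectomized rats.

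Items 196 and 197 are thus neither human nor observational, so the argument that observational effects are underestimates cannot apply to them. The other values in 7.1 are human but concern different outcomes: 2.3 is "for the effect of E2 replacement decreasing appetite in women with and without major depression", and 1.51 is for Lupron and food cravings.

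**The case against.** The strongest reply is that nothing is miscalculated. Both power figures reproduce, 7.1 openly states the .05 level and that .77 was worked back from the sample size, and this is a pilot. Under the pattern the protocol expects, with E2 protective and P4 exacerbating, the loss is one or two points at df 14. At df 28 power stays just above 80%. A q of .10 would leave it at about 79% or more. On the source of 1.5, the sentence supporting the 90% figure says only that it averages previous studies, and the section also credits human pilot work.

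Most of this stands, and it limits the point. A reader might infer that power at .77 is below 80% for every planned test, or that it collapses because only one of many effects may be real. The documents support neither reading: the first needs a df and a q that the plan does not state, and exactly one real effect among an outcome's three Aim 1 contrasts is impossible. A reader might also infer that the conclusion of sufficient power for E2 on binge eating fails. It does not fail if d = 1.5 is true.

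The reply does not rescue the scope of the .77 statement, which is given for two aims whose tests are all to be corrected. Nor does it rescue the description of the three references as human observational studies.

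**Conclusion.** The point holds as a mismatch between 7.1 and the plan's own tests and references, and it is minor to should-fix. The 80% at .77 is the power of one unadjusted paired contrast with 15 completers, not of the BH-corrected tests of Aims 1 and 2. In the Aim 1 scenarios examined at q = .05, the corrected power for E2 versus Lupron-alone runs from about 67% to about 82%. The range is driven by df and by whether P4 has an effect. It rests on equal SDs, families of three or six tests, and an assumed q.

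The power above 90% is right as arithmetic and robust to correction, but conditional on d = 1.5, whose stated origin does not match two of its three references. Those two were judged by title only. Which source yields 1.5 cannot be established from the documents, so it should not be inferred that the value was taken from rats.

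**What to change.** 1. In 7.1, label .77 as the detectable dz for a single unadjusted contrast with 15 completers. In 7.2, state the BH family and q. Restate power for that family using the planned model's df and the actual dependence among the contrasts. Figures that treat the contrasts as freely varying, with all of them or only one of them real, should not be used. An optional alternative is to name one primary Aim 1 outcome and contrast tested at .05, with BH on the rest; .77 is then correct for that test.
2. In 7.1, reconcile the description of the sources with references 196 and 197 by changing either the wording or the citations. State which source gives 1.5 and how it was derived. Drop the underestimate argument for the rat experiments, and say that 2.3 and 1.51 concern appetite and food cravings. Present the 90% figure as conditional on d = 1.5, with power at smaller effects beside it (for example d = 1.0: 95% unadjusted, 77% at .05/6).

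The cost is text only: no extra participants, and no change to the analysis beyond stating the family and q unless the optional alternative is taken. The stated power becomes slightly less favourable.

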7.2 Statistical Methods

Statistical analyses are completed using the most recent version of R. Primary outcome measures, as described below, are binge eating and aspects of the reward response. Methods are modeled after similar, successfully implemented studies.^{87, 117} All measures included are empirically valid, and well-established, thus, measures will be scored according to standard conventions and scoring procedures. Descriptive statistics and graphics will be used to screen for errors, outliers, and potential influential observations and to check distributional assumptions. Where appropriate statistical estimates will be tabulated. We first complete analysis without covariates. As appropriate, relevant covariates may also be included in data analysis (e.g., negative affect, self-reported food intake).

PRIMARY OUTCOMES

Binge eating will be defined as: 1) the EPSI subscale binge eating score obtained at each study visit (T1-T4), which represents a continuous score of symptoms over the previous week (higher scores indicate more symptoms); 2) a weekly average based on daily frequency obtained from the DSRP. For both the subscale score and weekly average, the primary outcome is the last week of each phase of the hormone challenge to capture the period of time with maximal symptom change.

Reward response will be defined by the Monetary Incentive Delay (MID),¹⁷⁴ the Delayed Discounting (DD), and Go No/Go behavioral tasks and the BIS/BAS and SPSRQ self-report questionnaires. MID operationalizes reward response as *motivated behavior*: the average speed of responses to reward vs. non-reward trials during a reward task.

DD operationalizes reward response as “delay gratification”: the tendency to choose small, immediate rewards over larger, delayed rewards. The task determines the rate of devaluation over time for the larger, delayed reward, which is defined as the k parameter. We use behavioral tasks of monetary reward vs. food because the value of food is dependent on hunger state^{202, 203} and it reduces the confounding effect of the task provoking symptoms.³⁴

The Go/No Go Task is a behavioral measure of inhibitory control. Inhibitory control is defined by the response accuracy of the go no/go trials with fewer errors (“go” response on a “no/go” trial) indicating better inhibitory control.

The BIS/BAS and SPSRQ will be included as a self-report measures of reward response. Specifically, we will include the reward responsiveness, behavioral inhibition, and fun seeking subscales of the BIS/BAS as self-report correlates of the reward response. The SPSRQ will be used to assess sensitivity to reward.

Hypothesis. Our overarching hypothesis for the following aims is that BN represents a hormone sensitive phenotype and this sensitivity is displayed as an impaired reward response within the context of low E2 such that E2 addback will be beneficial for all outcomes of interest (i.e., binge eating, aspects of the reward response). As such, our null hypothesis is that there is no effect of E2 on binge eating or the reward response. For all hypothesis tests, we will use the Benjamini-Hochberg Procedure to correct for multiple comparisons.

Aim 1: Quantify the direct effect of E2 and P4 on binge eating in women with BN.

Dependent variables: EPSI binge eating subscale score; DSRP binge eating weekly average.

Independent variables: Treatment sequence, treatment condition, and selected covariates

The two longitudinal measures of binge eating (i.e., EPSI subscale score and DSRP weekly average) will be fit to linear mixed effect models with subject-specific random intercept assuming an unstructured covariance among different time points. Such a covariance allows different variance and covariance parameters to be estimated for each time point allowing for potential increasing or decreasing variability in outcomes during each of the follow-up time points for each outcome and will include fixed effect predictors such as binary treatment sequence (E2-P4 or P4-E2) and treatment condition of categorical variable with three levels: Lupron-alone, E2, or P4, where effect size and standard error of fixed effect parameters will be estimated in the described model followed by t -test. Study hypotheses comparing outcomes between group outcomes of E2 vs. Lupron-alone, E2 vs. P4, and P4 vs. Lupron-alone, will be tested using contrasts test through t -test of least squares means estimate in the context of the main effects model.

Along with the primary contrasts of interest described above, additional contrasts between each end point of treatment condition (Lupron-alone, E2, or P2) and baseline (T1), which occurs prior to medication administration, will be tested using the statistical model just described above.

Aim 2: Determine the effect of E2 on reward response and related correlates (e.g., behavioral inhibition) in women with BN.

Dependent variables: Behavioral measures of reward response, self-report measures of reward response.

Independent variables: Treatment sequence, treatment condition, and selected covariates

Behavioral measures of reward response (MID, DD) and related correlates (Go No/Go, BIS/BAS, SPSRQ) will be fit to linear mixed effect models as described above with binary treatment sequence (E2-P4 or P4-E2), treatment condition, and covariates as independent variables and reward response as dependent variables. The contrasts between E2 and baseline (T1) or Lupron-alone (T2) will be tested in the same model.

For the behavioral tasks, beneficial impacts of E2 are defined as an accelerated speed of response to rewards and improvement in reward learning during the MID, higher indifference points during the DD task, and fewer errors on the Go No/Go Task. For self-report questionnaires, a decrease in scores represents a beneficial response as higher scores indicate more “pathological” responses.

Aim 3: Examine the association between reward response (defined in Aim 2) and binge eating before and after E2 addback.

Null hypothesis: There is no association between reward response and binge eating before and after E2 addback
Alternative hypothesis: There is an association between reward response and binge eating before and after E2 addback.

We will explore Pearson correlations between change in self-reported reward responses and change in binge eating between baseline and E2 addback. Binge eating will be defined by the EPSI subscale score. Reward response will include the BIS/BAS reward responsiveness subscale, and SPSRQ reward sensitivity subscale. Specifically, a change score will be created that signifies the amount and direction of change that occurred in binge eating and reward responses between baseline and E2 addback for each subject. A Pearson correlation will then be examined between binge eating and reward response change scores.

If Aims 1 and 2 alternative hypotheses are supported, we will conduct a tertiary exploration to address whether changes in reward behavior mediate the link between E2 addback and changes of binge eating. A four-step mediation analysis (Baron & Kenny 1986) will be applied to preliminarily investigate the mediation effect of reward-motivated behavior on changes of binge eating. An approximated t-test will be used to test the significance of the mediation effect.

Missingness. We will use multiple imputation to correct for data determined to be missing at random. Data for any dropouts will be compared with data for those who complete the study to determine the extent to which excluding their data will introduce selection bias, and selection bias will be identified as a weakness in any resulting publications or presentations.

Sensitivity Analysis. In addition to the statistical tests described above, we will use sensitivity analyses to evaluate the robustness of the main results of the study to reasonable perturbations of the statistical methods and assumptions used and to help ensure reproducibility of the main results. Sensitivity analysis will address the inclusion/exclusion of questionable data values (i.e., outliers), the use of alternative methods of coping with missing values and dropouts, and modeling assumptions. We will additionally examine whether associations differ based on the severity (e.g., DSM-5 mild, moderate, severe, extreme) of baseline binge eating and purging frequency.

